10.6. Physical Exam

Physical exam data for each subject will be presented in a listing.

APPENDIX 1. IMPUTATION ALGORITHM FOR PARTIAL AND MISSING DATES

This section describes missing date imputation methods.

For Adverse Events

If onset date is completely missing, onset date is set to date of first dose.

If (year is present and month and day are missing) or (year and day are present and month is missing):

- If year = year of first dose, then set month and day to month and day of first dose
- If year < year of first dose, then set month and day to December 31.
- If year > year of first dose, then set month and day to January 1.
- If month and year are present and day is missing:
 - If year = year of first dose and
 - If month = month of first dose then set day to day of first dose
 - If month < month of first dose then set day to last day of month
 - If month > month of first dose then set day to first day of month
 - If year < year of first dose then set day to last day of month
 - If year > year of first dose then set day to first day of month

For all other cases, set onset date to date of first dose.

For Concomitant Medications

Start Date: If start date is completely missing and end date is not prior to date of first dose, then the medication will be classified as concomitant. If start date is completely missing and end date is prior to date of first dose, then the medication will be classified as prior.

If (year is present and month and day are missing) or (year and day are present and month is missing) then set month and day to January 1. If year and month are present and day is missing then set day to first day of month.

End Date: If end date is completely missing then the medication will be classified as concomitant.

If (year is present and month and day are missing) or (year and day are present and month is missing) then set month and day to December 31. If year and month are present and day is missing then set day to last day of the month.

Note: that if both start and end dates are missing then the medication will be classified as concomitant.

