#### **10.1.6. Treatment-Emergent Adverse Events (TEAEs)**

An AE is defined as treatment emergent if the first onset or worsening is after an administration of study drug and not more than 7 days after the last dose. Any AEs that are deemed to be treatment related by the investigators will always count as TEAEs. The primary safety assessments will be based on TEAEs. For completeness, a listing of all reported AEs will be presented in the clinical study report (CSR).

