### 10.2.3. Documentation

All AEs occurring within the period of observation for the study must be documented in the eCRF with the following information, where appropriate (the period of observation for the study is described in [Section 10.2.](#)):

- AE name or term.
- When the AE first occurred (start date).
- When the AE stopped (stop date or an indication of "ongoing").
- Severity of the AE.
- Seriousness (e.g., hospitalization or death).

- Actions taken.
- Outcome.
- Investigator opinion regarding the AE relationship to the study drug(s).

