10.2. Adverse Events

Each AE and SAE term will be recorded as a verbatim term on the case report forms (CRFs). All AEs and SAEs will be coded by primary system organ class (SOC) and mapped to a preferred term using the MedDRA dictionary Version 22. The investigator will assess AE severity and relationship to the study treatment.

All AEs will be listed. However, only treatment emergent adverse events (TEAEs) will be included in the AE summaries. A TEAE is defined as any AE with an onset date in the interval between the first study treatment dosing date and 7 days after the last study treatment dosing date. In addition, any AEs occurring after the first dose that the investigators deem to be treatment related will also be considered TEAEs and will be included in the AE summaries.

For the purpose of calculating treatment emergence and inclusion in summary tables, incomplete onset dates will be imputed using the method described in [Appendix 1](#).

AEs will be summarized by the number and percentage of subjects in each primary SOC and preferred term. Subjects will be counted only once for each primary SOC and each preferred term. Summary tables of AEs by primary SOC, preferred term and severity will be provided. If a subject has more than one AE coded to the same preferred term, the subject will be counted only once for that preferred term by using the event with the highest severity. Similarly, if a subject has more than one AE within a primary SOC category, the subject will be counted only once in that SOC category by using the event with the highest severity. AEs by primary SOC, preferred term and relationship to study drug will be provided as well. In addition, serious adverse events (SAEs) by primary SOC and preferred term will be provided. Deaths and SAEs will be summarized similarly to AEs. All adverse event tables will also include the total number of events, counting multiple events per Subject.

In the AE summary, preferred terms within each SOC will appear in frequency order.

Frequencies for deaths and hospitalizations will also be summarized by treatment group and overall.

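### SAP Appendix 1 ignores the recorded stop date, so some incomplete onsets turn an adverse event that ended before dosing into a TEAE

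*SAP*

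**What the plan says.** The AE part of SAP Appendix 1 works from the onset date alone:

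- Nothing known: "If onset date is completely missing, onset date is set to date of first dose".
- Month missing: "If year = year of first dose, then set month and day to month and day of first dose"; but "If year < year of first dose, then set month and day to December 31".
- Only the day missing, in the first-dose year: "If month = month of first dose then set day to day of first dose"; an earlier month gets its last day.
- A residual rule sends anything not covered to the first-dose date. A record with the year missing but a month or day present would fall here.

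SAP 10.2 gives these dates their force: "For the purpose of calculating treatment emergence and inclusion in summary tables, incomplete onset dates will be imputed using the method described in" Appendix 1. It defines a TEAE by an onset from the first dosing date to 7 days after the last.

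The protocol definition (10.1.6) is: "An AE is defined as treatment emergent if the first onset or worsening is after an administration of study drug", again with a 7-day limit after the last dose. Events the investigator judges treatment-related always count.

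The stop date is available. Among the items Protocol 10.2.3 lists for the eCRF, where appropriate, is one that begins "When the AE stopped (stop date or an indication of" and goes on to allow for events still ongoing. The medication part of Appendix 1 does use the end date: "If start date is completely missing and end date is prior to date of first dose, then the medication will be classified as prior".

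**The concern.** An event that is known to have ended before the first dose cannot have begun or worsened after it. Imputing its onset to the first-dose date overrides a recorded fact and produces an event that starts after it stops. Because SAP 10.2 reads treatment emergence from that imputed date, the event enters the TEAE tables, and TEAE incidence is the primary safety variable (Protocol 12.1.1). No other sentence in the SAP corrects the result. The medication rule shows that the end-date check was thought of for one type of record and not carried over to the other.

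**Working it through.** The plan gives no figure for this point, so there is none to reproduce. The check applies the written rules to example records and then scales the effect.

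**1. Literal application.** Assume a first dose on 15 Jun 2021 and, for each record, a recorded AE stop on 10 Jun 2021. Both dates are illustrative.

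| Recorded onset | Imputed onset | SAP 10.2 result |
|---|---|---|
| Nothing known | 15 Jun 2021 | TEAE |
| 2021 only | 15 Jun 2021 | TEAE |
| Jun 2021 | 15 Jun 2021 | TEAE |
| Jun, year missing (residual rule) | 15 Jun 2021 | TEAE |
| May 2021 | 31 May 2021 | not a TEAE |
| Dec 2020 | 31 Dec 2020 | not a TEAE |
| 2020 only | 31 Dec 2020 | not a TEAE |

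The first four rows have an onset 5 days after the recorded end. In the last three the onset stays before the first dose. A stop date earlier in May would still precede the imputed 31 May, but the classification would not change.

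**2. How often the rule misfires, given such a record.** Assume that the true onset is uniform from 2 to W days before first dose, that the event ended before first dose, and that first-dose dates are uniform over the 365 days of 2021. There are 365 × (W − 1) combinations of first-dose date and lag.

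- Onset completely missing: always flagged, 100% for any W.
- Year only: an onset k days back escapes only when the first dose falls in the first k days of the year. Escapes total 2 + … + W = W(W + 1)/2 − 1.
  - W = 7: 27/2,190 escape, so 98.8% are flagged.
  - W = 30: 464/10,585 escape, so 95.6% are flagged.
  - W = 90: 4,094/32,485 escape, so 87.4% are flagged.
- Month and year: an onset k days back escapes when the first dose falls in the first k days of a month, with k capped at the length of that month.
  - W = 7: 12 × 27 = 324 of 2,190 escape, so 85.2% are flagged.
  - W = 30: 12 × 464 − 3 (for a 28-day February) = 5,565 of 10,585 escape, so 47.4% are flagged.
  - W = 90: 15.5% are flagged, by the same count.

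These shares are conditional on a pre-dose event being in the database with that onset pattern. They say nothing about how many such records there are.

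**3. Effect per record.** Take the Safety Population as the planned enrolment of about 150 (Protocol 12.2).

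- One subject added to a preferred term Overall: 1/150 = 0.67 percentage points. Three subjects: 2.0. Five subjects: 3.3.
- The SAP also tabulates by group, without giving group sizes. For an assumed group of 50, one subject is 1/50 = 2.0 points.
- Overall TEAE incidence changes only if the subject has no other TEAE in up to 15 months of treatment.
- The total number of events, which SAP 10.2 adds to every AE table, rises by one per record in any case.

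**The case against.** The strongest objection is that the triggering record lies outside planned collection. Protocol 10.2 collects AEs only once study drug has been given, and both schedules of assessments leave the AE row blank at Visit 1. The documentation duty in Protocol 10.2.3 covers the same period. A pre-dose AE in the database would be an anomaly for data-management queries, although no specific check is documented. This largely stands, and it keeps the point small. It does not repair the rule, which would still misclassify such a record if one reached analysis.

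The medication comparison is also weaker than it looks. Prior medications are collected by design (Protocol 8.12), so that rule has to separate prior from concomitant. It shows that the check is easy to write, not that many AE records need it.

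The bias is upward, which is conservative for safety, and TEAEs are summarised without a planned hypothesis test. Both are true. Conservatism justifies imputing an unknown date towards treatment; it does not justify overriding a known stop date.

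Three stronger readings are tempting, and the documents do not support them:

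- That every missing or partial onset is affected. The lower rows of the first check show otherwise.
- That the error is concentrated in Rollover subjects, whose TRD-201 events sit close to the first dose. Both schedules mark with an asterisk the assessments done as part of the TRD-201 End of Study visit, and the AE row carries no such mark. Nothing says that resolved TRD-201 events are copied into this study.
- That the earlier-year and earlier-month branches show the SAP expects events that resolved before dosing. They concern early onset, and would serve equally for events still ongoing at the first dose.

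**Conclusion.** The point holds in a narrow form. In four branches of the AE algorithm the first-dose date is assigned even when the recorded stop date is earlier, and SAP 10.2 then counts a TEAE that does not meet the onset-or-worsening test in Protocol 10.1.6. The size is at most 0.67 percentage points per record for a preferred term Overall, on the assumption of 150 subjects in the Safety Population. The effect on overall TEAE incidence is that amount or nothing. The number of such records is not in the documents and is probably close to zero, given when AE collection starts. Any error overstates harm. This is a stated rule that gives a wrong answer, not a threat to the study's conclusions, and should be treated as a minor correction.

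**What to change.** Add one sentence before the AE onset rules in Appendix 1, in the version finalised before database lock:

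*If, after query confirmation, the AE stop date (or the latest date consistent with a partial stop date) is before the date of first dose, the first-dose default is not applied, the imputed onset may not be later than the stop date, and the AE is not treatment-emergent unless it counts as a TEAE under the treatment-related provision of Protocol 10.1.6.*

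Leave every other rule as it is. Using the latest date consistent with a partial stop date keeps all uncertain cases as TEAEs. The closing exception is needed because Protocol 10.1.6 always counts treatment-related events; without it the sentence would create a new conflict.

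The cost is one programming condition and one query per affected record, with no new data collection. The downside is a small risk that a mis-entered stop date removes a true TEAE. Since AEs are collected only after dosing, a pre-dose stop date may itself be the mistake. The query limits that risk, and the listing of all AEs keeps the event visible.
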